3.2 Case Numbers and Grouping Methodology

The study anticipates enrolling 20 subjects with obsessive-compulsive disorder (OCD), all of whom will be assigned to the intervention group for treatment. This is an exploratory clinical study conducted as an open-label trial.

Sample size calculation was performed using G-Power 3.1 with the following parameters:

Effect size d: 1.0

Significance level α : 0.05 (two-tailed)

Power (1- β): 0.95

The calculated minimum sample size required is approximately 16. Considering a 20% clinical attrition rate, 20 participants are planned for enrolment.

IV. Inclusion and Exclusion Criteria

4.1 Inclusion Criteria

- 1) Volunteer subjects with Obsessive Compulsive Disorders (OCD) according to the Diagnostic and Statistical Manual of Mental Disorders (DSM V) criteria;
- 2) Age 18–60 years, right-handed;
- 3) Disease severity: Yale-Brown Obsessive Compulsive Scale score ≥ 16 for OCD patients;
- 4) Medication stable for at least 4 weeks;
- 5) Resistant patients to standard treatments: partial but insufficient response (reduction of Y-BOCS score $< 35\%$) or lack of response to previous well conducted treatment including: optimal tolerated dose and adequate duration (> 12 weeks) of at least 2 Serotonin Reuptake Inhibitors (selective serotonin reuptake inhibitors, clomipramine), or 1 Serotonin Reuptake Inhibitors + 1 augmentation strategy (adjunction of an antipsychotic - such as risperidone or olanzapine or aripiprazole - or lithium or buspirone)
- 6) No systematic rTMS therapy in the past six months;
- 7) Signature of informed consent form;
- 8) Normal vision or corrected vision;
- 9) Capacity to complete protocol-specified tests.

4.2 Exclusion Criteria

- 1) Abnormal cognitive status (assessed using MoCA with score < 24);
- 2) Other primary diagnosis than OCD (comorbid mild depression is tolerated)
- 3) Comorbid diagnosis of schizophrenia/ psychotic disorder, bipolar disorder, substance abuse or dependence3)
- 4) Significant self-harm intent or severe suicidal tendencies within the past year;

- 5) Irreversible visual or auditory impairment preventing completion of scales or related assessments;
- 6) Presence of metallic implants, such as pacemakers or stents;
- 7) Any current or potential medical, psychological, social, or geographical factors compromising patient safety or study participation;
- 8) Poor compliance;
- 9) Claustrophobia;
- 10) History of epilepsy or familial epilepsy
- 11) Pregnant or lactating women (women of childbearing potential must obtain a negative pregnancy test result prior to study commencement and employ medically approved contraceptive measures);
- 12) Deterioration or failure of vital organ function (cardiac, pulmonary, hepatic, renal, etc.); or unstable vital signs;
- 13) Conditions unsuitable for this stimulation site, such as increased intracranial pressure, elevated intraocular pressure, or glaucoma
- 14) History of or concomitant neurological disorders: cerebrovascular disease, central nervous system infections, Creutzfeldt-Jakob disease, Huntington's disease and Parkinson's disease, Lewy body dementia, traumatic brain injury dementia, other physical/chemical factors (drugs, alcohol, CO, etc.), significant somatic diseases (hepatic encephalopathy, pulmonary encephalopathy, etc.), intracranial space-occupying lesions (subdural haematoma, brain tumours), endocrine system disorders (thyroid disease, parathyroid disease), and dementia caused by vitamin deficiency or any other cause

V. Endpoints

5.1 Primary Endpoint

Obsessive-compulsive symptom severity: Yale-Brown Obsessive Compulsive Scale (Y-BOCS)

5.2 Secondary Endpoints

Clinical Global Impression Scale (CGI)

Depressive Symptom Severity: Hamilton Depression Rating Scale (HAMD-17 items)

Anxiety Symptom Severity: Hamilton Anxiety Rating Scale (HAMA-14 items)

Impulse Control Scale (UPPS-P)

Short-Form Parenting Behaviour Questionnaire (s-EMBU-C)

5.3 Safety Endpoints

Severity of Clinical Symptoms

5.4 Exploratory Endpoints

Beck Depression Inventory (BDI)

Chinese Version State-Trait Anxiety Inventory (STAI-S, STAI-T)

Chinese Version of the Obsessive-Compulsive Inventory (Revised) (OCI-R)

Intolerance of Uncertainty Scale (IUS-12)

Intolerance of Uncertainty Questionnaire (IUI-A, IUI-B)

Stress Perception Scale

Snaith-Hamilton Pleasure Scale (SHAPS)

Aphasia Evaluation Scale (Self-Report Version) (AES-S)

Physiological Data: Imaging and EEG require signal-to-noise ratios within acceptable ranges. Excessive head motion and motion artefacts may compromise data quality.

Data significantly affected (e.g., imaging head motion impacting image clarity, electrophysiological artefacts exceeding 20% of data) will be excluded.

Cognitive Behavioural Data.

All behavioural data exceeding three standard deviations above or below the mean will be excluded to prevent statistical bias.

VI. Adverse Event Collection and Reporting

6.1 Definition of Adverse Events

Adverse Event (AE): An undesirable medical occurrence in a patient or clinical trial subject following treatment, not necessarily causally related to the treatment. An adverse event may therefore be an undesirable and unexpected sign, symptom, or time-related condition associated with use, irrespective of causality to the treatment.

Serious Adverse Event (SAE):

- 1) Resulting in death;
- 2) Resulting in a serious deterioration in the subject's health:
 - a) Life-threatening illness or injury, or
 - b) Permanent impairment of a bodily structure or bodily function, or
 - c) Hospitalisation or prolongation of hospitalisation, or
 - d) Medical or surgical intervention to avert a life-threatening illness or injury, or to prevent permanent impairment of a bodily structure or bodily function
 - e) Fetal distress, foetal death, congenital malformation, or birth defect

Note: Hospitalisation previously planned for the current medical condition or steps required by the clinical study protocol, without significant deterioration in health, shall not be considered a serious adverse event.

When completing the adverse event form, the investigator shall use mild, moderate, or severe to describe the intensity of the adverse event. To standardise criteria, the grading of event intensity is as follows:

Mild: Subjective discomfort not requiring symptomatic treatment or intervention suspension. Examples include mild headache, fatigue, slight itching or tingling at the

stimulation site, photopsia, or minor facial muscle twitching. Such events cease upon intervention cessation.

Moderate: Subjective discomfort requiring intervention suspension but not special symptomatic treatment, as such adverse events cease shortly after intervention cessation. Examples include severe headache, significant stinging sensation or muscle twitching at the stimulation site, and other adverse events reported as intolerable.

Severe: Risk of disability or death requiring emergency treatment and immediate intervention cessation. Examples include epileptic seizures.

6.2 Recording and Reporting of Adverse Events

Adverse events occurring during clinical research must be reported by research personnel to the clinical research sponsor and the principal investigator's institution within 24 hours of becoming aware of the event. For mild or moderate adverse events, the study physician may document the event in detail and report it to the principal investigator within three days, provided the event has been adequately resolved and the subject's condition has improved and recovered. For serious adverse events, the investigator shall notify within 24 hours of becoming aware of the event and immediately complete an adverse event form, documenting the time of occurrence, severity, duration, measures taken, and outcome.

For any SAE occurring during the clinical trial (regardless of whether related to the trial or investigational device), the investigator shall immediately provide appropriate treatment to the subject while completing an SAE report form and submitting a written report to the principal investigator. The SAE must also be recorded in the AE report section of the Case Report Form (CRF).

The Principal Investigator shall submit a written report to the relevant Ethics Committee within 24 hours of receiving the SAE report form. For any fatality, the investigator shall provide all required documentation to both the Ethics Committee and the sponsor.

Adverse events (AEs) in this study specifically refer to any unfavourable medical events occurring in clinical research subjects during the intervention period, which need not necessarily have a causal relationship with the treatment. To ensure the

completeness of safety data collection, all adverse events occurring during the study must be recorded on the CRF, including those occurring during treatment and during the protocol-specified period after treatment. This encompasses all AEs not yet present prior to the initial visit and all AEs that recur or worsen after the initial visit.

Subjects may report AEs spontaneously. When documenting AEs, the investigator should use comprehensive diagnostic or standard medical terminology to describe symptoms, rather than recording individual signs or symptoms. The CRF and source documentation must be consistent. Any discrepancies between lay language in subject records (e.g., subject diaries) and corresponding medical terminology should be clarified in the source documentation.

AEs should be followed up until resolution, stabilisation, or when the investigator deems them no longer clinically significant, or until loss to follow-up. For a subject where an AE persists at the end of the study, follow-up should continue until resolution, stabilisation, or when the investigator deems it no longer clinically significant, or until loss to follow-up. If follow-up is not conducted, the investigator must provide justification. Follow-up shall typically continue for 30 days after the subject ceases intervention treatment. Where necessary, the investigator may be requested to conduct examinations to obtain supplementary measurements and/or assessments.

6.3 Risks and Adverse Reactions

To date, among tens of thousands of subjects globally who have undergone transcranial magnetic stimulation, no cases of permanent brain damage attributable to its use have been reported. However, a small proportion of subjects may experience mild headaches and fatigue during stimulation; mild tingling or itching may occur at the stimulation site; and depending on the stimulation location, photopsia or facial muscle twitching may also occur. These symptoms can be managed by adjusting stimulation parameters and are transient adverse reactions, resolving upon cessation of stimulation.

Beyond mild headaches, safety considerations for TMS encompass other factors documented in the literature. For instance, epileptic seizures may occur, typically in individuals with pre-existing brain disorders, those using medications that lower the

seizure threshold, or those with a history of alcohol abuse. Therefore, in addition to screening criteria requiring the absence of any neurological or psychiatric conditions and no family history of epilepsy, this study will also exclude any individuals at risk of seizure induction due to epilepsy medications or alcohol consumption, thereby minimising the likelihood of epileptic seizures.

The transcranial magnetic stimulation apparatus currently in our possession allows for parameter adjustment, fully conforming to the aforementioned specifications and constituting a highly safe device. Professional medical personnel will be present throughout the stimulation period. Should any participant experience a seizure during transcranial magnetic stimulation, we shall implement the following procedures:

- 1) Disconnect the power supply to the transcranial magnetic stimulator and immediately remove the stimulation coil from the participant's head.
- 2) Medical personnel will administer emergency treatment.
- 3) Family members will be notified.
- 4) Staff will accompany the subject to the nearest medical facility.
- 5) Medical expenses will be advanced by trial personnel and covered by the research organisation.
- 6) Referral to another hospital will be determined based on clinical necessity.

VII. Withdrawal Criteria

Subjects may withdraw from the study at any time for any reason. Investigators may withdraw subjects from the study at any time for any reason. If any medical condition or circumstance arises that renders continued participation in the study not in the subject's best interests, the research subject may withdraw from the study. Withdrawal from the study shall not prejudice any benefit to the subject. Following termination, no further data collection shall be conducted from the subject. Reasons for termination or withdrawal shall be documented on the Case Report Form (CRF).

Reasons for study termination include, but are not limited to:

- 1) Death of the subject.
- 2) Loss to follow-up.
- 3) Refusal by the subject to receive further treatment and/or follow-up, accompanied by withdrawal of informed consent.
- 4) Investigator termination of the subject's participation.
- 5) Adverse events (e.g., occurrence of intolerable adverse events or adverse event treatment necessitating withdrawal).
- 6) Serious protocol deviation.
- 7) Subject meeting exclusion criteria (newly emerging or confirmed).

Management of withdrawn subjects:

- 1) All original data for withdrawn subjects shall be retained. If withdrawal occurs due to reason 2, the investigator shall endeavour to contact the subject via multiple channels (e.g., telephone, text message) to ascertain the reason, conducting at least three attempts at follow-up and re-enrolment.
- 2) The timing and reason for trial discontinuation shall be documented in detail on the CRF.
- 3) For subjects withdrawing due to reason 5, adverse events must be appropriately managed, with follow-up continuing until the adverse event (AE) is resolved or stabilised.

VIII. Data Management

This project will utilise Case Report Forms (CRFs) for data recording. The CRF cover page shall display the clinical trial name, study site, subject name abbreviation and code, study start and end dates, and date of each interview to facilitate collation and organisation. The initial interview shall cover: demographic characteristics (pinyin initials, gender, age, ethnicity, etc.), general disease status (diagnosis, duration, etc.), past medical history, prior treatments (medication names, duration, dosage, etc.),

physical examination, and vital signs. Interviews shall occur during the baseline period, treatment completion period, and follow-up period. The CRF shall include clinical scales required by the study, to be assessed by a clinician. Except during the baseline period, each assessment requires recording the occurrence of adverse events on the case report form. If present, the adverse event report form must be completed in detail. Upon completion of the case report form, the investigator must enter the data into the study computer. Magnetic resonance imaging data and cognitive task data are stored on the study computer, named using the subject identification number and interview period, and saved in a specific format. Data entered into the computer may not be modified by any person during the study period.

This study protocol and data shall be accessible only to medical and statistical experts involved in this trial, participating investigators, and other trial personnel, as well as relevant institutions such as the healthcare facility conducting the trial and the ethics committee. Participants' personal information shall be strictly confidential, with data stored in encrypted computers using participant identification numbers. Data transfer shall be conducted by researchers via encrypted portable hard drives.

Findings from this project may be published in medical journals. Patient information shall remain confidential in accordance with legal requirements and shall not be disclosed unless mandated by relevant legislation. Where necessary, governmental regulatory bodies, hospital ethics committees, and their authorised personnel may access patient records as prescribed.

IX. Statistical Analysis

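### Section 6.3 counts on a medication exclusion to limit seizure risk, but no criterion in Section IV names it and 6.3 words the group in two ways

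*Protocol*

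**What the plan says.** Protocol 6.3 names the people in whom seizures tend to occur: "typically in individuals with pre-existing brain disorders, those using medications that lower the" "seizure threshold, or those with a history of alcohol abuse" (one sentence, split by a page break). It then states the safeguards. One is described as already part of screening: "in addition to screening criteria requiring the absence of any neurological or psychiatric conditions and no family history of epilepsy". The other is presented as an addition: "this study will also exclude any individuals at risk of seizure induction due to epilepsy medications or alcohol consumption". From these together it concludes that the chance of a seizure is kept to a minimum.

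Section IV holds the criteria that a screener applies. On current medication, 4.1 item 4 says only "Medication stable for at least 4 weeks". Item 5 requires an insufficient response to earlier treatment with "at least 2 Serotonin Reuptake Inhibitors (selective serotonin reuptake inhibitors, clomipramine), or 1 Serotonin Reuptake Inhibitors + 1 augmentation strategy". Item 1 requires a DSM diagnosis of OCD, and 4.2 item 2 accepts mild depression alongside it. Section 3.2 confirms the population: "The study anticipates enrolling 20 subjects with obsessive-compulsive disorder (OCD), all of whom will be assigned to the intervention group for treatment".

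**The concern.** Section 6.3 is a risk narrative; Section IV is the operative list. If the narrative relies on an exclusion that the list does not contain, someone who follows Section IV correctly could admit a patient whom the safety section says is excluded. Two screeners could also read the promise differently, because the group is worded in two ways.

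The subject is not a trivial one. Section 6.1 gives epileptic seizures as its example of a severe adverse event, and every subject receives active stimulation: six sessions a day for five days, 30 in all (3.1). Section VII makes newly meeting an exclusion criterion a reason to end participation. It is therefore also unclear whether a change of medication during the study would count.

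**Working it through.** There is no figure in the plan to reproduce. The check sets each eligibility statement in 6.3 against the 9 items of 4.1 and the 14 items of 4.2 (9 + 14 = 23 items).

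| Statement in 6.3 | Counterpart in Section IV | Agreement |
|---|---|---|
| No family history of epilepsy | Exclusion 10 (personal or familial epilepsy) | Yes |
| No neurological condition | Exclusion 14 (list of neurological disorders) | Yes, in substance |
| Alcohol-related risk excluded | Exclusion 3 (diagnosed substance abuse or dependence) | In part |
| Medication-related seizure risk excluded | None of the 23 items names it | No |
| No psychiatric condition | Inclusion 1 requires OCD; exclusion 2 accepts mild depression | Contradicted |

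**Medication.** Three items come near and none of them fills the gap.
- Inclusion 4 concerns stability. It excludes no drug or drug class.
- Exclusion 7 covers medical and other factors that could compromise safety. It could be used to turn such a patient away, but it mentions neither medication nor seizures.
- Exclusion 14 contains the word drugs, but only inside its list of neurological disorders and their causes.

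**Wording of the group.** The risk sentence in 6.3 speaks of people using drugs that lower the seizure threshold. The exclusion sentence speaks of risk due to epilepsy medications. Taken literally, these are different groups. The context suggests that one group is meant, but the text does not say which wording governs.

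**Why it bears on this population.** Inclusion 5 selects patients with previous drug treatment, and inclusion 4 lets stable medication continue. The protocol does not say whether any drug that a candidate may be taking falls under the exclusion in 6.3.

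**Psychiatric wording.** Inclusion 1 makes the statement in 6.3 untrue of any eligible subject. Reading it as no psychiatric condition other than OCD does not rescue it, because exclusion 2 accepts mild depression.

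**The case against.** The best defence is that this is a matter of placement. Section 6.3 is itself protocol text and announces the exclusion as additional to the screening criteria, so a list without it is not strictly in conflict with it. Exclusion 7 gives an investigator a route to apply it, and the two wordings may be loose drafting. Compliance could be checked from source data, since the initial interview in Section VIII records past history and medication names, duration and dosage.

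Part of this stands. The commitment does exist in the document, and the data to apply it would be collected. But a discretionary clause that does not name the group is no substitute for a specific promised exclusion, and recorded medication names cannot settle compliance until the protocol says which medication counts.

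A reader might infer three stronger things that the documents do not support.
- *That the eligibility statements in 6.3 disagree with Section IV as a whole.* They do not: the family-history and neurological statements have counterparts, and so in part does the alcohol statement.
- *That most or all subjects will be taking a drug that 6.3 means to exclude.* Inclusion 5 concerns earlier treatment and says nothing about current use. The protocol nowhere classes the drugs listed there as affecting seizure threshold.
- *That the psychiatric phrase would misdirect screening.* Inclusion 1 and exclusions 2 and 3 set the psychiatric rules plainly, and psychiatric illness is not among the risk groups that 6.3 names. On its own the phrase is close to a clerical error.

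**Conclusion.** Wrong as written, and it should be corrected before enrolment. The main point is that the medication exclusion on which 6.3 partly rests its seizure-risk conclusion appears in none of the 23 eligibility items and is worded inconsistently within 6.3. The lesser point is that the phrase about psychiatric conditions contradicts inclusion 1 and exclusion 2.

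The size can be stated only as this textual gap. The documents give no seizure rate and no expected number of patients on relevant medication, so neither a change in risk nor a number of wrongly admitted patients can be derived. The conclusion assumes that Section IV is the list screeners use and that the exclusion in 6.3 is meant to be binding. Both are the natural reading of the text.

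**What to change.** Reconcile 4.1, 4.2 and 6.3 before enrolment, so that the risk section and the eligibility list state the same medication exclusion in one consistent wording and it is clear whom it covers, given that inclusion 4 allows ongoing stable medication. In the same revision, bring the psychiatric wording of 6.3 into agreement with inclusion 1 and exclusion 2. Which clinical rule applies is for the investigators to decide.

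The cost is an edit to the protocol and one line on the screening checklist. The medication history needed is already recorded at the initial interview (Section VIII). Depending on how the sections are reconciled, somewhat fewer patients may be eligible.

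### Section VII bars data collection after any termination, so consenting subjects lose their remaining Y-BOCS ratings and the ban conflicts with the adverse-event follow-up required elsewhere

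*Protocol*

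**What the plan says.** Section VII (Withdrawal Criteria) states: "Following termination, no further data collection shall be conducted from the subject". Seven reasons for termination follow. Only reason 3, refusal of further treatment or follow-up, is described as "accompanied by withdrawal of informed consent". Reasons 4 to 7 are investigator termination, adverse events, serious protocol deviation, and an exclusion criterion that emerges or is confirmed later.

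Under the management of withdrawn subjects, item 1 keeps data already recorded and, for subjects lost to follow-up, asks for contact, "conducting at least three attempts at follow-up and re-enrolment". Item 3 requires management of adverse events after reason 5, "with follow-up continuing until the adverse event (AE) is resolved or stabilised".

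Section 6.2 applies to all subjects: "Follow-up shall typically continue for 30 days after the subject ceases intervention treatment", and "If follow-up is not conducted, the investigator must provide justification". It also requires that "all adverse events occurring during the study must be recorded on the CRF", including events in the specified period after treatment.

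Section 3.1 gives treatment over five consecutive days, with symptom ratings before and after the course and at two and four weeks after treatment. Section 5.1 names the Y-BOCS as the primary endpoint.

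**The concern.** Two things are at stake.

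- **Primary-endpoint data.** A rating that the protocol forbids collecting cannot be recovered by any analysis plan. In a single-arm study no comparison group would show that losses were selective. If subjects terminated under reasons 4 to 7 respond worse than the rest, the pre-post change among those who remain is too favourable.
- **Safety data.** Staff who obey the ban would stop recording adverse events at termination. Staff who obey Section 6.2 and item 3 of Section VII would continue. Both instructions are in force.

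A related gap is that Section VII does not say outright whether a subject who stops stimulation but remains willing to be assessed counts as terminated. Site staff need that answer before they can apply the ban.

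**Working it through.** **1. Which subjects the ban reaches**

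| Reason | Consent withdrawn by definition? | Further ratings possible? | Adverse-event follow-up required by |
|---|---|---|---|
| 1 Death | not applicable | no | not applicable |
| 2 Loss to follow-up | no | only if contact is regained | Section 6.2, until lost |
| 3 Refusal | yes | no | Section 6.2, or justification |
| 4 Investigator decision | no | yes | Section 6.2 |
| 5 Adverse event | no | yes | Section VII item 3 and Section 6.2 |
| 6 Serious deviation | no | yes | Section 6.2 |
| 7 Exclusion criterion | no | yes | Section 6.2 |

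The avoidable loss of ratings is in rows 4 to 7. The conflict over adverse-event data is clearest in row 5, where Section VII contradicts itself. In rows 4, 6 and 7 the follow-up duty rests on Section 6.2 alone.

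**2. The plan's own figures**

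Section 3.2 gives d = 1.0, two-sided alpha 0.05, power 0.95, 20% attrition. An exact paired t-test gives power 0.949 at n = 15 and 0.962 at n = 16, so the minimum is 16. Then 16 / 0.8 = 20, which reproduces the planned enrolment. The allowance equals 0.20 × 20 = 4 subjects, not broken down by reason.

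**3. Size of a possible bias**

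Assumptions, none of them in the documents: improvement in SD units is N(mu, 1); a share p of subjects is lost under this rule, p = 5% (1 of 20) or 10% (2 of 20); the odds of loss multiply by OR for each SD of worse response. The model is logit P(lost) = a − ln(OR) × (improvement − mu), with a solved so that overall loss equals p. Bias is the mean improvement of those remaining minus mu, by numerical integration. Completer d is (1 + bias) / completer SD at mu = 1.

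| p | OR | Bias (SD) | Completer SD | Completer d |
|---|---|---|---|---|
| 5% | 1 | 0 | 1.000 | 1.00 |
| 5% | 2 | 0.034 | 0.989 | 1.04 |
| 5% | 3 | 0.051 | 0.976 | 1.08 |
| 5% | 5 | 0.068 | 0.959 | 1.11 |
| 10% | 1 | 0 | 1.000 | 1.00 |
| 10% | 2 | 0.066 | 0.981 | 1.09 |
| 10% | 3 | 0.098 | 0.959 | 1.14 |
| 10% | 5 | 0.127 | 0.933 | 1.21 |

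With no true change, simulated two-sided rejection by the paired t-test among completers is 5.2 to 5.9% at p = 5% and 5.8 to 8.0% at p = 10%, for OR 2 to 5.

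**4. Comparison with sampling error**

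The 95% half-width in SD units is t / √n: 2.093 / √20 = 0.468 and 2.110 / √18 = 0.497. The largest bias, 0.127, is about a quarter of 0.497. Power at d = 1.0 is 0.989 with 20 subjects and 0.979 with 18, so power is not the issue.

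**5. What collecting the ratings would recover**

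If a random half of the lost subjects attend and their ratings are used, the remaining bias is (1 − p) × bias / 2 / (1 − p/2). For p = 10% and OR 5 this is 0.90 × 0.127 / 2 / 0.95 = 0.060. The range over OR 2 to 5 is 0.02 to 0.03 SD at p = 5% and 0.03 to 0.06 SD at p = 10%.

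**6. Visit timing**

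For a subject who stops on day s, a four-week visit counted from planned day 5 falls 5 + 28 − s = 33 − s days after the last session: 32 days for s = 1, 28 for s = 5. Counted from the last session it is always 28.

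**The case against.** **Adverse-event follow-up is provided for.** A reader might infer from the ban that the protocol leaves no room for it after termination. That is not so: item 3 of Section VII and Section 6.2 both require it, and a specific rule placed after a general one is often read as its exception. This stands as far as it goes. The finding is a conflict in wording, not an absent provision, and even a generous reading of item 3 rescues only reason 5 and only adverse events. Nothing rescues the Y-BOCS ratings.

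**Stopping treatment is partly distinguished from leaving.** Reason 3 makes refusal a termination only when consent is also withdrawn, reason 5 concerns events that necessitate withdrawal, and Section 6.2 speaks separately of ceasing treatment and of the end of the study. This too stands: the distinction is implied, but Section VII does not state it.

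**Weaker conflicts should not be pressed.** Contact attempts after loss to follow-up serve to learn the reason and regain the subject, so they hardly contradict the ban. Section VIII ties adverse-event recording to each assessment, but a cancelled visit does not by itself remove the record, because Section 6.2 independently requires all events on the CRF.

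**The bias is assumed and small.** Correct. The documents give neither the loss by reason nor its relation to response. For subjects who finish the five days, the end-of-treatment comparison is untouched.

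**Conclusion.** The concern holds as a minor one. As worded, Section VII discards obtainable primary-endpoint ratings from subjects who have not withdrawn consent, and it contradicts the adverse-event follow-up in its own item 3 and in Section 6.2. Those two statements rest on the text alone.

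The statistical consequence depends on assumptions: 0.03 to 0.13 SD towards benefit if 1 to 2 of 20 subjects are lost with odds 2 to 5 times higher per SD of worse response, and zero if loss is unrelated to response. Set against a half-width of 0.47 to 0.50 SD in an exploratory study, this would not overturn a conclusion. A reader might infer that the trial's result is seriously biased or underpowered by this rule; the documents do not support either reading. Nor does changing the rule guarantee an unbiased estimate: the bias falls only if these subjects attend and the analysis uses their ratings.

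**What to change.** Amend Section VII in three places.

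1. Limit the ban on further data collection to subjects who withdraw informed consent.
2. State whether stopping stimulation alone counts as termination. Add that subjects whose stimulation or participation ends for reasons 4 to 7, with consent still in force, are asked to attend the remaining scheduled Y-BOCS and adverse-event assessments, where they agree and the investigator considers attendance to be in their interest. Naming reasons 4 to 7 keeps death and loss to follow-up out of the rule.
3. State the anchor for the two-week and four-week visits (last session received, or planned end of the course). Section 6.2's 30 days is a typical period for adverse-event follow-up, so a visit at day 31 or 32 would breach nothing. The anchor is needed so that visits are comparable across subjects.

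Separately, reconcile the ban with the adverse-event follow-up in item 3 of Section VII and in Section 6.2, including what applies after consent is withdrawn. No change to clinical care or to when stimulation stops is proposed. Whether the extra ratings enter the primary comparison, including those of subjects found ineligible under reason 7, can be left to the SAP.

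The cost is a few sentences and the visits of perhaps 1 to 2 subjects on the assumption above. The estimate may also be slightly less favourable, because it would include subjects who received only part of the 30 sessions.
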